### **8.4.1 Packaging and Labeling**

The UCSF Investigational Drug Service (IDS) will receive the bulk supplies of spironolactone and matching placebo from the compounding pharmacy. Capsules will be stored, accounted for, assigned per the randomization schedule and packaged and labeled for dispensing to the subject by the IDS pharmacy staff once ordered by the investigator on a study order/prescription form.

The IDS generates labels in compliance with California State pharmacy regulations, e.g., bottles will bear the name and address of pharmacy, name of subject, date of dispensing, name of the prescriber, instructions for use, expiry date and name, strength and quantity of the material dispensed. Capsules will be labeled as “spironolactone or placebo” to maintain the blind.

### **8.4.2 Storage**

Study drug will be stored by the study site at controlled room temperature, 15 to 30°C (59 to 86°F). If the temperature of the study drug storage exceeds or falls below this range, this will be reported to the Sponsor or designee and captured as a deviation. Subjects will be instructed to store the medication in original packaging (plastic bottles and protected from light) at room temperature according to the instructions outlined on the Drug Administration Instructions.

### **8.4.3 Dispensing**

An order form/prescription will be sent to the IDS pharmacy. Drug will be selected, counted and labeled by the IDS staff based on the randomization schedule. Labeled bottles will be picked up from the pharmacy by the investigator’s staff and dispensed to the subjects by the research staff during a study visit. Participants will receive 3 month supplies.

## **8.5 Dosage Regimen**

Participants will take either spironolactone or placebo by mouth once daily in the morning. Morning is preferred due to the diuretic effect of spironolactone, which may be less convenient at nighttime. Absorption is not affected by fasting state therefore participants may take this with or without food.

## **8.6 Administration Instructions**

At the participant’s baseline visit she will receive the pill bottle and be shown the pills with instructions on how to take this.

## **8.7 Study Drug Accountability**

An accurate and current accounting of the dispensing and return of study drug for each subject will be maintained on an ongoing basis by a member of the study site staff. The number of study drug dispensed and returned by the subject will be recorded on the Investigational Drug Accountability Record.

## **8.8 Measures of Treatment Compliance**

Subjects should be instructed to retain all bottles of investigational product, even if empty, and to return them to the Investigator at the indicated visits. The Investigator or designee should perform investigational product accountability (i.e., count of returned capsules) and, if applicable, follow-up with the subject to retrieve any investigational product bottles that have not been returned. If the Investigator has concerns about a subject's dosing compliance, she should discuss this with the subject, assess the reasons for noncompliance and the likelihood that the subject will remain noncompliant, and notify the Sponsor accordingly.

# **9 STUDY PROCEDURES AND GUIDELINES**

A Schedule of Events representing the required testing procedures to be performed for the duration of the study is diagrammed in Appendix 1.

Prior to conducting any study-related activities, written informed consent and the Health Insurance Portability and Accountability Act (HIPAA) authorization must be signed and dated by the subject. If appropriate, assent must also be obtained prior to conducting any study-related activities.

## **9.1 Clinical Assessments**

### **9.1.1 Concomitant Medications**

All concomitant medication and concurrent therapies will be documented at Screening and at all subsequent in person study visits and at early termination when applicable. Dose, route, unit, frequency of administration, indication for administration, and dates of medication will be captured.

### **9.1.2 Demographics**

Demographic information (i.e. date of birth, race, ethnicity) will be recorded at Screening.

### **9.1.3 Medical History**

Relevant medical history, including history of current disease, alcohol use, and other pertinent information regarding underlying diseases will be recorded at Screening.

### **9.1.4 Physical Examination**

A complete physical examination will be performed by either the investigator or a subinvestigator who is a physician or other licensed medical professional at Screening. An abbreviated physical examination tailored to the symptoms the subject reports will be done at all subsequent in person visits. New abnormal physical exam findings must be documented and will be followed by a physician or other qualified staff at the next scheduled visit.

### **9.1.5 Vital Signs**

Body temperature, blood pressure, pulse and respirations will be performed after resting for 5 minutes at all in person study visits.

### **9.1.6 Anthropomorphic measures**

Height will be measured at Screening. Weight will be measured at all in person study visits. Waist circumference will be measured at all in person study visits.

### **9.1.7 Adverse Events**

Information regarding occurrence of adverse events will be captured throughout the study. Duration (start and stop dates), severity/grade, outcome, treatment and relation to study drug will be recorded on the case report form (CRF).

## **9.2 Clinical Laboratory Measurements**

### **9.2.1 Blood Chemistry Profile**

Blood will be obtained and sent to the site's clinical chemistry lab for determination of serum sodium, potassium, creatinine at in person study visits. Liver tests (aspartate aminotransferase (AST/SGOT), alanine aminotransferase (ALT/SGPT), alkaline phosphatase, total bilirubin, and direct bilirubin), hemoglobin A1c, glucose, insulin, and lipid panel will be performed at each visit.

### **9.2.2 Pregnancy Test**

Women of childbearing potential are required to perform a pregnancy test every 4 weeks. A urine pregnancy test will be obtained from participants of childbearing age prior to their participation in the study and at every in person study visit. Women who are not sexually active with men may decline the urine pregnancy test.

Home pregnancy test kits will be supplied at each visit to women of childbearing potential and these are to be performed as per the kit instructions every 4 weeks between study visits from Day 1/Baseline to End of Study/End of Treatment.

The site will call the participant every 4 weeks in between visits to record the result of the home pregnancy test. In the event of a positive result the patient must discontinue study drug immediately and report the result to the site as soon as possible.

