### **5.3 Safety Evaluations**

- In-person visits will be conducted at baseline, at one month (given highest risk of adverse events in first month of drug exposure) and every 3 months thereafter. Additionally women will be seen within 3 months after end of treatment to ensure resolution of any drug related side effects. In-person study visits will include a physical exam with vital signs, anthropomorphic measurements, assessment of adherence with pill counts, assessment of side effects, and performance of safety monitoring labs including electrolytes, renal function and urine pregnancy tests. Each visit will also include contraceptive counseling for pre-menopausal women because spironolactone has potential risk of feminization seen in animal studies of male fetuses, though no studies have implicated spironolactone in these birth defects in humans. Pregnancy testing will be performed every month to ensure that if a participant were to become pregnant, spironolactone is discontinued within 4 weeks of conception. This will ensure no fetal risks as human sex organ development begins between 6-8 gestational weeks.
- There will be continuous safety surveillance of participants through the reporting of incidence of adverse events (AEs). AEs will be recorded in a systematic manner at every study visit and when otherwise volunteered by the participant.

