### **9.4 Magnetic Resonance Imaging**

Liver stiffness assessments will be performed by MRE (shear wave 60 Hz) and MRI-PDFF at the Baseline/Day 1 Visit, Month 6, and Month 12 (if subject opts to extend to 12 months). The MRE and MRI-PDFF assessments will occur sequentially. The scans will be read by a radiologist in the UCSF Department of Radiology & Biomedical Imaging.

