### **10.2 Visit 2 (Day 1/Baseline)**

- Record any Adverse Experiences.
- Concomitant medications review.

- Assess liver stiffness by MRE and MRI-PDFF
- Randomize to treatment group, dispense study drug, and provide instructions on how to take it.

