## APPENDIX 1. Schedule of Events

	Screening	Baseline/ Day 1	Month 1	Month 3	Month 6 End of Study/ Treatment	Month 9*	Month 12* End of Study/ Treatment	Follow-Up within 3 months of EOS/EOT
	Visit 1	Visit 2	Visit 3	Visit 4	Visit 5	Visit 6	Visit 7	
Obtain informed consent	X							
Review your medical history	X							
Review medications you are taking	X	X	X	X	X	X	X	X
Perform complete physical exam	X							
Perform physical exam depending on your symptoms			X	X	X	X	X	
Measure your vital signs (blood pressure, heart rate)	X		X	X	X	X	X	
Measure your weight and height	X a		X	X	X	X	X	
Measure your waist circumference	X				X		X	
Review your general health (side effects and illnesses)		X	X	X	X	X	X	X
Draw samples of your blood for to check your general health, liver health, cholesterol, glucose, and insulin levels	X		X	X	X	X	X	
Draw samples of your blood to check your sex hormone levels	X				X		X	
If you are a female who can have children, collect a sample of your urine for pregnancy	X b		X	X	X	X	X	
Collect a small liver sample (biopsy)	X c				X*		X*	
Scan your liver: MRI-PDFF and MRE		X			X		X	
Give you study drug and instructions on how to take it		X	X	X	X	X	X	
Review the amount of study drug you have taken and collect unused			X	X	X	X	X	

a Height only measured at Screening

b In addition, home pregnancy tests are to be performed by women who can have children every 4 weeks from Day 1 until End of Study/Treatment

c Performed prior to screening as part of your standard of care for NASH

\*Optional visits/procedures

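### No pregnancy test is scheduled on the day drug is first dispensed, and 4-weekly testing does not deliver the promised four-week stopping limit

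*Combined protocol and SAP*

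**What the plan says.** **The rule.** Section 9.2.2 states of the urine pregnancy test that it "will be obtained from participants of childbearing age prior to their participation in the study and at every in person study visit". Those without male sexual partners may decline it.

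**Visit 2 is in person.** Section 5.3 says "In-person visits will be conducted at baseline, at one month". Section 8.6 has the woman attend: at her "baseline visit she will receive the pill bottle and be shown the pills with instructions on how to take this". Section 9.4 schedules "MRI-PDFF at the Baseline/Day 1 Visit".

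**The visit list and schedule.** Section 10.2 gives four items for Visit 2: adverse experiences, concomitant medications, the scans, and "Randomize to treatment group, dispense study drug, and provide instructions on how to take it". No pregnancy test appears. In Appendix 1 the row that begins "If you are a female who can have children, collect a sample of your urine for pregnancy" is marked at Screening and Months 1, 3, 6, 9 and 12, and is blank at Baseline/Day 1.

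**Home tests.** Section 9.2.2 places these "every 4 weeks between study visits from Day 1/Baseline to End of Study/End of Treatment", with results collected by telephone. Appendix 1, footnote b, has them "every 4 weeks from Day 1 until End of Study/Treatment".

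**The promised limit.** Section 2.1 describes 4-weekly testing and says drug would be stopped by week 4 after conception. Section 5.3 describes monthly testing, presents it as guaranteeing the same four-week limit, and concludes that there will be no fetal risk. Both rest on sex organ development beginning at 6-8 gestational weeks.

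**The concern.** There are two linked problems.

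1. The general rule in Section 9.2.2 covers the visit at which drug is first handed over, but the two places that staff work from leave the test out. Screening may last up to a month (Synopsis; Section 4.1), so the most recent negative result could be about a month old at first dispensing. No sentence requires a negative result before drug is dispensed.
2. The four-week limit is stated as something the schedule guarantees. A 28-day testing interval uses all 28 days, which leaves nothing for the time between conception and a test turning positive. The limit is also counted from conception while the window it protects is given in gestational weeks, and the protocol does not convert one to the other.

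What is at stake is fetal exposure to a drug that the protocol itself treats as a risk to male fetuses, and the accuracy of a safety statement that the ethics board relies on.

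**Working it through.** **Inputs from the protocol**
- Testing interval I: 28 days (Sections 2.1 and 9.2.2; Appendix 1, footnote b), or a calendar month (Section 5.3).
- Screening-to-Day-1 gap S: 0 to about 30 days.
- First on-drug home test: day 28.
- Stopping: immediate on a positive result (Section 9.2.2), so no further delay is added.
- Window: 6-8 weeks, or 42-56 days.

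**Assumptions, not in the protocol**
- Detection lag L, the time from conception until a urine test can be positive: 7-14 days, with L = 0 shown as the limiting case.
- Dating offset: 0 days (weeks counted from conception) or 14 days (gestational weeks run two weeks ahead of conception).

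**Step 1: the protocol's own figure.** Worst case from conception to detection = I + L. With I = 28, L = 0 and a negative test on Day 1, this is 28 days, so the stated limit is reproduced under those three conditions together.

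**Step 2: relax each condition.**

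| Setting | Formula | L = 0 | L = 7 | L = 10 | L = 14 |
|---|---|---|---|---|---|
| 28-day testing, Day 1 test done | 28 + L | 28 | 35 | 38 | 42 |
| 31-day month, Day 1 test done | 31 + L | 31 | 38 | 41 | 45 |
| No Day 1 test, S = 14 | 14 + 28 + L | 42 | 49 | 52 | 56 |
| No Day 1 test, S = 30 | 30 + 28 + L | 58 | 65 | 68 | 72 |

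Two breaches of 28 days need no assumed lag: the 31-day month, and any screening gap without a Day 1 test.

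**Step 3: compare with the window.** Counted from conception, 6-8 weeks is days 42-56 (offset 0) or days 28-42 (offset 14).
- No Day 1 test, S = 30: 58 + L is past day 56 for every L, so past the window under both conventions.
- Day 1 test done: 35-42 days is before or at the start of the window (offset 0), or inside it up to its end (offset 14).

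**Step 4: what a Day 1 test removes.** Conceptions before the first dose that would still be dispensed drug span S + L days without the test and L days with it. At S = 30 this is 37, 40 and 44 days against 7, 10 and 14. The reduction is 30/(30 + L) = 81%, 75% and 68%. At S = 14 the spans are 21-28 against 7-14 days. At S = 0 nothing is gained.

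**Step 5: how often the four-week limit would be missed, given conception on treatment.** Take conception as uniform over days 0-182, with the Day 1 test done and drug ending at day 182. A gap of g days between consecutive tests contributes max(0, g + L - 28) late days. The first gap (0 to 28) contributes none, because pre-dose conceptions are not counted here.
- Home tests every 28 days from Day 1, plus clinic tests (days 0, 28, 30, 56, 84, 91, 112, 140, 168, 182). The contributing gaps are 26, 28, 28, 28 and, at larger L, 21. Late days are 26, 41 and 61 for L = 7, 10 and 14, which is 14.3%, 22.5% and 33.5% of 182.
- Home-test count restarting at each visit (days 0, 28, 30, 58, 86, 91, 119, 147, 175, 182). There are five contributing gaps of 28, so late days are 5L = 35, 50 and 70, or 19.2%, 27.5% and 38.5%.
- At L = 0 both schedules give 0%.

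**The case against.** The strongest reply is that Section 9.2.2 already requires the Day 1 test, so this is a checklist slip and not a missing safeguard. Pregnancy is also an exclusion (Section 6.3), and a positive test stops drug at once. That is a fair description of the first part. But no text makes dispensing depend on a result, and staff work from the visit list and the schedule.

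Whether Visit 2 falls under the rule can be questioned. Section 4.1 does not name Day 1 among its in-person evaluations, and the procedure list in Section 5.3 is generic (it includes pill counts). Section 10.2 also omits vital signs, weight and waist circumference, which Sections 9.1.5 and 9.1.6 require at all in-person visits. Sections 5.3, 8.6 and 9.4 nevertheless put the woman at the site on Day 1. The other omissions show a wider Visit 2 mismatch and do not excuse this one.

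Home tests starting from Day 1 could be read as including one on Day 1. Section 9.2.2 places them between visits and reports them by telephone, so they are not a check before dispensing.

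On the numbers, the 58-72 day figures stack worst cases: a full month of screening, conception just after the screening test, and no test until day 28. The late shares depend on an assumed lag and testing grid. Only Section 5.3 says monthly; the other sections say four weeks. With a 14-day offset, day 28 after conception is exactly gestational week 6, so the limit and the window are compatible under that convention, though with no margin. All of this stands as qualification, and none of it makes the limit follow from the schedule.

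The Follow-Up visit also lacks the test (Section 10.5, Appendix 1), although Section 4.1 makes it in person. It comes after treatment ends, so it matters less.

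**Conclusion.** The concern holds and should be fixed. The inconsistency between Section 9.2.2 and Section 10.2 with Appendix 1 is certain and needs no outside figure. So is the failure of the four-week guarantee under calendar-month testing (31 days) or an untested 30-day screening gap (58 days), both at zero lag.

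The remaining figures rest on the assumed 7-14 day lag: a worst case of 35-42 days with a Day 1 test, and 14-38% of on-treatment conceptions detected after day 28 across the two testing grids. Those shares are conditional on conception and say nothing about how often it would occur. The birth control condition, counselling and 4-weekly calls make it less likely. Whether 35-42 days falls inside the sensitive window depends on a dating convention the protocol does not state. This is a participant-safety and consistency point; sample size and analyses are unaffected.

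**What to change.** - **Section 10.2 and Appendix 1:** add a urine pregnancy test at Visit 2, with a negative result required before drug is dispensed. Keep the Section 9.2.2 exception for women who may decline.
- **Section 5.3:** remove the claims that testing guarantees the four-week limit and the absence of fetal risk, and change the monthly interval to every 4 weeks.
- **Sections 2.1 and 5.3:** state the limit as four weeks plus detection lag, with the limit and the developmental window on the same dating convention. The clinical team should supply the lag and decide whether the resulting limit is acceptable.

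The cost is one line, one table mark, some rewording, and one urine test per woman of childbearing potential at Visit 2 (30 women planned), which Section 9.2.2 already requires. The stated safety limit becomes less favourable: 35-42 days under the assumed lag, in place of 28. Keeping 28 days would instead need testing every 28 - L days, which is every 21 days at L = 7 and every 14 days at L = 14.

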### **9.2.3 Sex Hormone Measurements**

A comprehensive panel of sex hormones (testosterone, androstendione, DHEAS, estrone, estradiol, follicle stimulating hormone, and sex hormone binding globulin) will be performed at baseline, Month 6, and Month 12 (if subject opts to extend the study period). These will be sent to the research laboratory of Dr.[name] at the University of Wisconsin National Primate Laboratory.

### **9.2.4. Constitution of biobank**

Samples of blood and liver tissue will be kept from patients who provide their written informed consent for the purpose of conducting future studies investigating the link between reproductive health in women and liver disease. An additional amount of blood (2 Tbsp) will be collected along with the main study lab samples at each visit. Approximately 1 cm of the 3 cm core of tissue obtained in the Month 6 (or Month 12)

End of Study/ End of Treatment Visit liver biopsy (optional procedure) will be stored in the biobank.

Specimens will be stored at the UCSF Clinical Research Services Moffitt site in a specimen bank. Specimens and certain non-identifying medical information may be shared with other scientists or companies not at UCSF.

### **9.4 Magnetic Resonance Imaging**

Liver stiffness assessments will be performed by MRE (shear wave 60 Hz) and MRI-PDFF at the Baseline/Day 1 Visit, Month 6, and Month 12 (if subject opts to extend to 12 months). The MRE and MRI-PDFF assessments will occur sequentially. The scans will be read by a radiologist in the UCSF Department of Radiology & Biomedical Imaging.

## **10 EVALUATIONS BY VISIT**

### **10.1 Visit 1 (Screening)**

- Review the study with the subject and obtain written informed consent and HIPAA authorization.
- Assign the subject a unique screening number.
- Record demographics data.
- Record medical history, in relation to inclusion/exclusion criteria.
- Record concomitant medications.
- Perform a complete physical examination.
- Perform and record vital signs (blood pressure, pulse), height, and weight.
- Measure waist circumference.
- Collect blood for clinical laboratory tests
- Collect urine sample and perform pregnancy test for women of childbearing potential.

### **10.2 Visit 2 (Day 1/Baseline)**

- Record any Adverse Experiences.
- Concomitant medications review.

- Assess liver stiffness by MRE and MRI-PDFF
- Randomize to treatment group, dispense study drug, and provide instructions on how to take it.

#### **10.3 Visits 3 – 4 (Months 1 and 3)**

- Record any Adverse Experiences.
- Record changes to concomitant medications.
- Perform abbreviated physical examination.
- Perform and record vital signs (blood pressure, pulse) and weight.
- Measure waist circumference.
- Collect blood for clinical laboratory tests.
- Collect urine sample and perform pregnancy test for women of childbearing potential.
- Perform pill count for compliance assessment.
- Collect all unused study drug.
- Dispense study drug.

#### **10.4 Visit 5 (Month 6 End of Study/Treatment)**

- Record any Adverse Experiences.
- Record changes to concomitant medications.
- Perform abbreviated physical examination.
- Perform and record vital signs (blood pressure, pulse) and weight.
- Measure waist circumference
- Collect blood for clinical laboratory tests
- Collect urine sample and perform pregnancy test for women of childbearing potential.
- Obtain liver biopsy (optional for subject).
- Assess liver stiffness by MRE and MRI-PDFF
- Perform pill count for compliance assessment.
- Collect all unused study drug.

#### **10.5 Visit 6 (Follow-Up)**

- Record any Adverse Experiences.
- Record changes to concomitant medications.

#### **10.6 Optional Visits (if subject opts to extend study period)**

- Month 9 visit will include the same evaluations as listed for Visits 3 and 4
- Month 12 Visit will serve as the end of study/treatment visit (liver biopsy will be completed at Month 12 instead of Month 6 if subject wishes to extend study period).

